Rotation groups (including 11 groups that each included 3–4 students) were randomly divided into one of two groups in ratio of 1:1 by the cluster randomization method, using a computer-generated random number table. The allocation process was conducted by a colleague who remained independent of this research project. The randomization result was concealed within serially numbered opaque envelopes, which were opened prior to teaching and lecture. One group was trained using direct laryngoscopy with a video laryngoscope (direct group), and the other group was trained using indirect (video) laryngoscopy with a video laryngoscope (indirect group). Cluster randomization was adopted to eliminate possible contamination between students due to individual randomization within each rotation. The blinding of participants and instructors was not possible due to the nature of the interventions

The study took place on the first day of the rotation. First, an initial evaluation of the students' intubation skills was performed on a standardized manikin (Laerdal® Airway Management Trainer, Laerdal, Stavanger, Norway) using a Macintosh laryngoscope (Diamond range; Penlon, Abingdon, UK; Macintosh blade size 3). The instructor evaluated each attempt and gave no feedback. Then, a lecture on airway anatomy, evaluation, and Cormack-Lehane classification (degree of glottis exposure), as well as airway management, was given, followed by tutorial videos on the technique of direct laryngoscopy and introduction of the McGrath[™] MAC video laryngoscope

(Medtronic, Minneapolis, MN, USA). Following the lecture, a teaching sequence with the McGrath[™] MAC video laryngoscope was conducted. All participants performed five intubations in the manikin using the McGrath[™] MAC video laryngoscope (blade size 3) with the instructor's direct feedback. The direct group intubated using the video laryngoscope as a direct laryngoscope, where only the instructor could observe the video screen and give feedback. The indirect group used the video laryngoscope as an indirect laryngoscope, so that they shared the video view with the instructor and received feedback.

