Then, a final evaluation was performed in which the students performed tracheal intubation using the Macintosh direct laryngoscope in the same manikin in the following scenarios: 1) normal airway in the supine position and 2) cervical immobilization with a semi-rigid foam neck collar (Philadelphia cervical collar; A-Mi Global, Busan, South Korea). Each student performed the intubation twice for each scenario, and the instructor evaluated each attempt. For all intubation attempts, a standard beveled Portex® tracheal tube (Smiths Medical, Hythe, UK; 7.0 mm internal diameter, 9.6 mm outer diameter) was used with a stylet inserted in the tube. The tube was bent into a "hockey-stick" curvature. The outcome assessors did not involve in training and were kept blinded to the allocation.

The primary endpoint was the intubation time, defined as the time taken from insertion of the blade between the teeth until the cuff of the tube was inflated. Unilateral bronchial intubation was considered successful for the purpose of this study. A failed intubation was defined as when it was not completed within 120 seconds or it resulted in an esophageal intubation. Additional data obtained included the rate of successful tracheal intubation, dental trauma, and degree of difficulty. Dental trauma was counted based on the number of audible teeth clicks (0, 1, and 2) in the Laerdal airway trainer. After the students completed the attempts, they were asked to score the degree of difficulty using each device with a 10-point numeric rating scale (NRS; 0 = easy, 10 = difficult).

Statistical Analysis Plan

All statistical analyses were performed using SAS version 9.4 (SAS Institute, Inc., Cary, NC, USA).

Data are presented as the mean and SD when normally distributed, as the median and interquartile range when non-normally distributed, and percentage when appropriate.

We used the linear mixed effects model to analyze intubation times and the degree of difficulty.

We also applied the generalized linear mixed model with binomial distribution and generalized estimating equations methods to analyze the intubation success rate.

As fixed effects, we included baseline intubation time, age, sex, group, manikin, time, and time by group interactions.

As random effects, we used a random intercept and slope for intubation time after education and a random intercept only for the degree of difficulty.

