The variance-covariance structures were chosen with the smallest Akaike Information Criterion criteria. In regard to the selection of working correlation matrix in the generalized estimating equations model, Quasi-likelihood under the Independence model Criterion was used to assess the goodness-of-fit. We also specified and partitioned different variance-covariance structures for each level of manikin. For comparing times before training with those after training, we used the paired t-test, Mann-Whitney U test, or McNemar's test, as appropriate. A *p*-value < 0.05 was considered statistically significant.

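### The GEE for intubation success names no small-sample variance correction, so an uncorrected Wald z test would reject a true null about 6–9% (students as clusters) or 10–14% (rotations as clusters) of the time

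*Combined protocol and SAP*

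**What the plan says.** The Statistical Analysis Plan applies a binomial mixed model and "generalized estimating equations methods to analyze the intubation success rate". The covariates are given once for all models: "As fixed effects, we included baseline intubation time, age, sex, group, manikin, time, and time by group interactions". The one sentence specific to the GEE concerns the "selection of working correlation matrix in the generalized estimating equations model, Quasi-likelihood under the Independence model Criterion was used to assess the goodness-of-fit". A p-value below 0.05 "was considered statistically significant".

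The Methods section gives the size of the trial: "Rotation groups (including 11 groups that each included 3–4 students) were randomly divided". It describes the allocation of these rotations as "into one of two groups in ratio of 1:1 by the cluster randomization method".

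The plan does not state the GEE variance estimator, any bias correction, the type of test, the reference distribution, or whether the GEE clusters on the student or the rotation. Success is listed among the additional data. The primary endpoint is intubation time, analysed by a linear mixed model.

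**The concern.** GEE inference usually rests on the empirical (sandwich) variance, which is valid when there are many clusters. With few clusters and several covariates that vary only between clusters, the fitted model follows the data too closely. The residuals are then too small, and so is the variance built from them. QIC chooses a correlation structure and leaves that bias in place.

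At stake are the p-value and confidence interval for the arm odds ratio on success. Without a correction, a chance difference between direct and indirect training would be called significant more often than the 0.05 rule implies, and the interval would be too narrow. The problem does not depend on correlation within rotations. It also bears on the natural analysis of a cluster-randomised trial: moving the GEE cluster from student to rotation makes the excess larger unless the variance is corrected.

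**Working it through.** The documents state no success rate, power or achieved error rate for this test, so the only figure to compare with is the nominal 0.05 (two-sided assumed).

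**Inputs from the documents**
- Rotations: 11, with 3–4 students each. Students: 11 × 3 = 33 to 11 × 4 = 44. A 1:1 split of 11 rotations is 6 against 5 at best.
- Outcomes after training: 2 scenarios × 2 attempts = 4 binary results per student.
- Coefficients: 7 listed terms + intercept = 8, if manikin and time each have two levels. Five are constant within a student (intercept, group, baseline time, age, sex).

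**Inputs assumed**
- Success 75–90% in the normal airway and 50–75% with the collar; student random-intercept SD 1–1.5 logits. Wider values were also tried, as shown below.
- No group effect, and rotation variance set to zero.

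**Why the variance is too small.** Write B = (Σ D′V⁻¹D)⁻¹ and, for cluster i, leverage H = D B D′V⁻¹ and residual r. The uncorrected sandwich is B (Σ D′V⁻¹ r r′ V⁻¹D) B, and r shrinks by roughly (I − H). The traces of H sum to the number of coefficients, 8. The average per cluster is therefore 8/44 = 0.18 to 8/33 = 0.24 for students, and 8/11 = 0.73 for rotations. Mancl-DeRouen replaces r by (I − H)⁻¹r; Kauermann-Carroll uses (I − H)^(−1/2) r.

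**Simulated type I error, uncorrected sandwich, reject if |z| > 1.96, eight coefficients**

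| Setting | Students as clusters | Rotations as clusters |
|---|---|---|
| Assumptions above, exchangeable, 3,000 trials each | 6.6–8.7% | 12.7–13.8% |
| Same assumptions, 2,000 trials each, group averaged over attempts | 6.4–8.2% | 11.2–13.0% |
| Same, group at the reference attempt | 5.1–6.8% | 9.5–11.5% |
| Success 80–85% / 60–65%, 33 and 38 students, 2,000 trials each | 6.8–7.6% | 11.5–12.9% |
| Success 60, 75 or 85%, SD 0–3, time as attempt or as pre/post, 2,000–4,000 trials each | about 7–9% (33 students), 6–7.6% (44) | mostly 11–13%, range about 9–14% |
| A further run, eight coefficients | 6.0–9.0% | 10.1–14.8% |

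Monte Carlo standard errors: √(0.08 × 0.92/4,000) = 0.4 points and √(0.12 × 0.88/2,000) = 0.7 points.

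The time-by-group interaction gave about 5–7% with students as clusters and 8.5–12.4% with rotations. With group and scenario as the only covariates, the group effect gave 5.3–6.6% and 10.8–11.7%. A robust score test on the full model gave about 5–7% with either unit.

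**With correction, group effect**

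| Variance and reference | Students | Rotations |
|---|---|---|
| Mancl-DeRouen, z | 2.2–5.0% | 3.3–6.4% |
| Kauermann-Carroll, z | 4.6–6.0% | 6.7–8.6% |
| Kauermann-Carroll, t (n − 5 df for students; 11 − 2 = 9 df for rotations) | 3.7–5.0% | 3.6–5.1% |
| Mancl-DeRouen, t | about 1–3.5% for either unit | (same) |

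The correction and the reference distribution have to be named together. With 11 clusters, Kauermann-Carroll with z still over-rejects, and Mancl-DeRouen with t over-corrects.

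**The case against.** The strongest reply is that the plan is silent, and silence is not a choice. A reader might infer that the plan commits to an uncorrected sandwich and so has a fixed error rate above 5%. The documents do not support that. They name no variance estimator, test, contrast or cluster unit, and a robust score test would come close to nominal. This stands, and the point is therefore conditional. But nothing in the plan excludes the uncorrected Wald test, and a score p-value would not widen an interval built from the uncorrected standard error.

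The eight coefficients are also an inference. The plan does not define time, and the covariate list is worded as for a mixed model, so fitting all of it in the GEE is a reasonable reading but not a stated one. With students as clusters, a reduced model or a group coefficient at one reference attempt brings the rate close to 5%. With rotations as clusters, even the reduced model gave 10.8–11.7%.

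A reader might also infer that the trial's main result is at risk. It is not: success is an additional endpoint and is analysed by a binomial mixed model as well. That limits the consequence. It does not make the GEE p-value correct, and the plan does not say which of the two success analyses governs.

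Finally, with students as clusters, Mancl-DeRouen can trade mild inflation for conservatism of similar size. That is a fair reason to choose the cluster unit and reference distribution deliberately.

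**Conclusion.** The point holds as a conditional one. If the GEE uses the usual uncorrected sandwich with a Wald z test and fits all the listed fixed effects, the test of the group effect on success has a true error rate of about 6–9% with 33–44 students as clusters. With the 11 rotations as clusters it is about 10–14%, roughly two to three times nominal. Some settings fall outside these ranges: down to 5.1% and 9.5% for the group effect at the reference attempt, and up to 14.8% for rotations.

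The direction is consistent across all the assumptions tried; the exact rates are not fixed by the documents. Because rotation variance was zero throughout, this is a separate matter from whether correlation within rotations is modelled. It is worth correcting because the remedy is cheap.

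**What to change.** After the QIC sentence in the Statistical Analysis Plan, add a sentence such as:

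> For intubation success, the GEE cluster is the randomised rotation. Standard errors, confidence intervals and p-values use a bias-corrected sandwich variance (Mancl-DeRouen with a normal reference, or Kauermann-Carroll with a t reference on 9 degrees of freedom) in place of the uncorrected empirical variance.

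One of the two pairings should be fixed in advance. The same sentence should state the group contrast to be tested (averaged over attempts or at a named time) and whether the full covariate list applies to the GEE.

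The cost is one sentence, a change in the analysis code and no new data. The plan names SAS 9.4 but no procedure, so the statistician should confirm that the procedure used offers the chosen correction. The interval becomes slightly wider. If students were kept as the clusters with Mancl-DeRouen, the test would be mildly conservative, at about 2–5% actual error.

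### The Statistical Analysis Plan names the Mann-Whitney U test, which assumes independent samples, as the only rank test for before-versus-after times in the same students; a paired rank test is needed (minor)

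*Combined protocol and SAP*

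**What the plan says.** Under Methods, the study day opens with a baseline assessment: "an initial evaluation of the students' intubation skills was performed on a standardized manikin", using a Macintosh laryngoscope. The number of baseline attempts is not given; the text says only "The instructor evaluated each attempt and gave no feedback". After the lecture and five practice intubations, "a final evaluation was performed in which the students performed tracheal intubation using the Macintosh direct laryngoscope in the same manikin". There are two final scenarios, a normal airway and "cervical immobilization with a semi-rigid foam neck collar", and "Each student performed the intubation twice for each scenario". The collar is mentioned only at the final evaluation.

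The Statistical Analysis Plan analyses intubation time, the primary endpoint, with a linear mixed model: "As fixed effects, we included baseline intubation time, age, sex, group, manikin, time, and time by group interactions". A separate sentence near the end covers the before-after comparison: "For comparing times before training with those after training, we used the paired t-test, Mann-Whitney U test", or McNemar's test, whichever suits. No paired rank test is named anywhere in the plan.

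**The concern.** The sentence is confined to times before training against times after it. Each student supplies both, so the data come in pairs. Two of the three listed tests (paired t and McNemar) respect this. Mann-Whitney U does not: it treats the before and after values as coming from different people. Leaving the choice to what is suitable does not help, because an independent-samples test is never the matching choice for this comparison.

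The non-parametric option is a real one. The plan provides for medians and interquartile ranges when data are not normal, and intubation times with a 120-second limit may well be skewed. If the option was used, the p-value for improvement with training comes from a test that ignores each student's own baseline. When a student's two times are positively correlated, such a test is too conservative and can miss a modest improvement.

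The sentence is loosely drafted in another way. It speaks of times, yet McNemar's test is for paired binary outcomes and can apply only to success or failure.

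**Working it through.** The plan states no sample size, SD, correlation or effect size, so there is no figure of its own to reproduce.

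**Inputs from the documents.** The Methods describe rotation groups "including 11 groups that each included 3–4 students". That gives 11 × 3 = 33 to 11 × 4 = 44 students. The significance level is 0.05; two-sided testing is assumed.

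**Assumed inputs.** One before and one after value per student; within-student correlation ρ of 0.3, 0.5 or 0.7; log-normal times; shifts of 0.4, 0.6 or 1.0 SD of log time; no failed attempts; no clustering in steps 1 to 3.

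**Step 1: type I error by formula.** An unpaired comparison takes the variance of the difference as 2σ²/n. With pairs it is 2σ²(1 − ρ)/n. The true level is therefore about 2 × [1 − Φ(1.96/√(1 − ρ))]:

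| ρ | 1.96/√(1 − ρ) | Level |
|---|---|---|
| 0 | 1.96 | 5.0% |
| 0.3 | 2.34 | 1.9% |
| 0.5 | 2.77 | 0.6% |
| 0.7 | 3.58 | 0.03% |

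**Step 2: type I error by simulation of the rank tests.** Mann-Whitney gives about 2%, 0.7% and 0.1% at ρ = 0.3, 0.5 and 0.7. The signed-rank test gives about 5% throughout. At ρ = 0 both are close to 5%. Only a negative correlation would push Mann-Whitney above its level (about 7% at ρ = −0.2).

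**Step 3: power.** A normal-theory check for n = 33, ρ = 0.5 and a shift of 0.4 SD:
- Unpaired: 0.4/√(2/33) = 1.62. The true SD of the statistic is √0.5 = 0.71, so power ≈ Φ((1.62 − 1.96)/0.71) = Φ(−0.47) ≈ 32%.
- Paired: 0.4/√(2 × 0.5/33) = 2.30, so power ≈ Φ(2.30 − 1.96) = Φ(0.34) ≈ 63%.

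Simulated power of the rank tests at ρ = 0.5 is somewhat lower but shows the same gap:

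| n | Shift | Mann-Whitney | Signed-rank |
|---|---|---|---|
| 33 | 0.4 SD | 29% | about 55% |
| 44 | 0.4 SD | 42% | 70% |
| 33 | 0.6 SD | 69% | 89% |
| 44 | 0.6 SD | 84% | 96% |
| 33 or 44 | 1.0 SD | over 99% | over 99% |

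**Step 4: clustering, a side issue.** If changes are correlated within rotation groups, a simple paired test is mildly anti-conservative. The design effect is 1 + (m − 1) × ICC. It is 1.10 for m = 3 and an assumed ICC of 0.05, and 1.60 for m = 4 and an ICC of 0.20. Putting 1.96/√(design effect) into the step 1 formula gives levels of about 6% and 12%. Simulation agrees: 5.6–11.7% for signed-rank and 6.0–12.1% for the paired t-test already in the plan. A t-test on the 11 group-mean changes holds 4.8–5.1%.

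**The case against.** The strongest reply is that this is a slip of the pen: the neighbouring tests are both paired, so the authors probably meant a Wilcoxon test and may have run one. The option may never have been used. Training effects in novices may also be large, and at 1 SD either test would detect them. All of that stands, and it is why the point is minor. It does not make the sentence right, and anyone reproducing the analysis would follow the name given.

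The simulations also leave out failed attempts (over 120 seconds or esophageal), which could produce capped or missing times. The figures show direction and rough size, not what happened in this trial.

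A reader might infer three stronger things that the documents do not support:
- **Inflated false positives.** This would need repeat attempts to be pooled as independent values. No section describes pooling, and the number of baseline attempts is not stated.
- **That these tests are the only analysis of improvement.** The mixed model includes a time effect and its interaction with group, and time is never defined. Baseline time is a covariate, which suggests that the model covers post-training times only, but a before-after reading is not excluded.
- **That a mixed model of the change with a rotation-group effect is required.** In simulation such a model is itself conservative (3.0–4.4%) and in some settings gains no power over Mann-Whitney (80% for both at n = 44, ICC 0.20, 0.6 SD). Clustering affects the listed paired t-test equally and is a separate matter.

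**Conclusion.** The concern holds, as a minor one. The test named does not match the paired design wherever the non-parametric option is used, and the documents do not say whether it was. With one value per student per time and positive within-student correlation, the effect is conservatism and lost power for modest shifts. It disappears as the correlation approaches zero and has no practical consequence when the shift is about 1 SD. Correlations, shifts and ICCs are all assumed; only the 33 to 44 students and the 0.05 level come from the plan. The between-arm mixed-model analysis of the primary endpoint does not use this test and is unaffected.

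**What to change.** In the Statistical Analysis Plan:
- Replace the Mann-Whitney U test with the Wilcoxon signed-rank test for before-after times.
- Define one before and one after summary per student, since there are two final attempts per scenario, and say how a failed attempt enters it.
- Restrict the comparison to scenarios with a baseline measurement; none is documented for the collar.
- State that McNemar's test applies to success, not to times.
- Re-run any before-after comparison that used Mann-Whitney.

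Optionally, add a check that respects the rotation groups, such as a t-test on the 11 group-mean changes. If the comparison is made within each arm, a 1:1 split leaves only 5 or 6 groups (4 or 5 degrees of freedom), so this check would be weak there.

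The cost is one changed phrase, a sentence or two of definition and possibly a short re-run. No new data are needed.
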